- Impact of Events Scale-Revised (IES-R) subscales, Appendix J: 15 items, answered on a 5-point scale ranging from “not at all” to “extremely” with higher scores indicating greater distress (worse outcome).
- PROMIS General Self-Efficacy and Self-Efficacy for Managing Emotions subscales, Appendix K: 16 items, answered on a “I am not at all confident” to “I am very confident” with higher scores indicating greater self-efficacy (better outcome).
- eHealth Impact Questionnaire (e-HIQ), Part 1 and 2, Appendix L: 26-item measure, answered on a 5-point scale with higher scores indicating a greater, more positive impact.
- COmprehensive Score for Financial Toxicity (COST), Appendix M: 10-item measure, answered on a 5-point scale ranging from “not at all” to “very much” with higher scores indicating greater financial toxicity (worse outcome).
- InCharge Financial Distress/Financial Well-being, Appendix N: 8-item measure, answered on a 10-point scale with response options varying across items (eg, “overwhelming stress” to “no stress at all” and “worry all the time” to “never worry”) with higher scores indicating better financial well-being (better outcome).
- Uncertainty Management Preferences Scale, Appendix O: 15-item measure, answered on 7-point scale from ‘strongly disagree’ to ‘strongly agree’ with higher scores indicating a stronger preference.
- Brief Health Literacy Screener, Appendix P: 3-item measure, answered on a 5-point scale ranging from “always” to “never” with higher scores indicating better health literacy (better outcome).
- Health Literacy Screening Questionnaire, Appendix Q: 8-item measure, answered on 4- and 5-point scales with response options varying across items (eg, “very bad” to “very good”; “disagree strongly” to “agree strongly”; and “never” to “always”) with higher scores indicating better health literacy (better outcome).

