Illness Perceptions Questionnaire-Revised (Appendix H): ²⁴ Validated measure of cognitive and emotional representations of illness. Items were adapted to refer to participants' infertility risk. 5 subscales will be used (5 to 6 items each; 28 items total): Personal control, Treatment control, Illness coherence, Consequences, and Emotional representations. Items are answered on a 5-point scale from "Strongly Agree" to "Strongly Disagree," with higher scores indicating worse outcomes. Each subscale is scored separately, and averages are calculated. The IPQ-R has been validated in cancer populations.	X	X	X
Reproductive Concerns after Cancer Scale (Appendix I): ²⁵ Validated, 18-item measure of AYA-F cancer survivors' fertility and health concerns with 6 subscales: Concerns about fertility potential, Partner disclosure, Becoming pregnant, Child's health, Personal health, and Acceptance. Answers are on a 5-point scale, "Strongly Disagree" to "Strongly Agree" with higher scores indicating more concern (worse outcome). Mean scores are calculated, ranging from 1 to 5.	X	X	X
Impact of Events Scale-Revised (Appendix J): ²⁶ The IES-R is a validated measure of distress in reaction to negative life events and will be adapted to measure current subjective distress related to infertility risk. The Intrusive Thoughts (7 items) and Avoidance (8 items) subscales assess intrusive thoughts and effortful avoidance of reminders about a distressing event, respectively. Answers are on a 5-point scale: "Not at all" to "Extremely."	X	X	X
PROMIS Self-Efficacy (Appendix K): ²⁷ The PROMIS General Self-Efficacy and Self-Efficacy for Managing Emotions subscales measure the degree to which people feel confident in managing various situations, problems, and events and confidence in managing difficult emotions. Questions will assess general self-efficacy in these domains and self-efficacy in managing fertility and family-building issues and emotions.	X	X	X

	Timepoint		
	T1: baseline; pre-intervention	T2: 1-month post-baseline	T3: 3-months post-baseline

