For **Study Objective 2**, for each outcome variable, we will examine the distributional qualities, extent of missing data, and satisfaction of assumptions of randomness (ie, MAR, MCAR). Descriptive statistics will evaluate sample characteristics. Covariates with significant relationships with the decisional conflict scale (DCS) will be included in final models. To obtain an effect size estimate of the decision aid in reducing decisional conflict, pairwise t-test will evaluate change in DCS mean scores from T1 to T2. A two-sided hypothesis test of the within-subject difference in adjusted means will test the null hypothesis ($H_0: \mu_1 = \mu_2$) at $\alpha = 0.05$. Rejection of the null hypothesis will indicate a significant within-subject DCS mean change from T1 to T2 ($H_1: \mu_1 > \mu_2$). Effect size estimates (Cohen’s d) will be calculated and reported. On an exploratory level, we will examine T1 to T3 and T2 to T3 mean differences to characterize the DCS trajectory. Similar procedures will analyze changes in the IPQ-R, RCACS, PROMIS Self-Efficacy, and the IES-R as secondary outcomes, controlling for key covariates. The Stage of Decision Making Scale will be assessed, and descriptive statistics will evaluate whether use of the decision aid website impacts readiness to engage in decision making, progress in making a choice, and receptivity to considering or re-considering options between timepoints T1 and T2 and between timepoints T2 and T3. The Preparation for Decision Making Scale will be assessed, and descriptive statistics will evaluate whether use of the decision aid website impacts perception of how useful a decision aid or other decision support intervention is in preparing the respondent to communicate with their practitioner at a consultation focused on making a health decision. The eHealth Impact Questionnaire-Part 2 will be assessed and descriptive statistics will evaluate the impact of using the decision aid website across three domains: 1) confidence and identification of health concerns, 2) information and presentation of website material, and 3) understanding and motivation to manage health issues.

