Description: The Reproductive Concerns After Cancer (RCAC) Scale is a validated survey of cancer survivors’ fertility and health concerns. The survey has 18 questions, answered on a 5-point scale ranging from (1) “strongly disagree” to (5) “strongly agree.”

Total scores range from 18 to 90, with higher scores indicating greater distress (worse outcome). The outcome will be reported as the mean difference from baseline to 1 and 3 months, with standard deviation.

Timeframe: 3 months

Outcome 5 (Secondary)

Title: Impact of Events Scale-Revised (IES-R)

Description: Impact of Events Scale-Revised (IES-R) is a validated measure of distress in reaction to negative life events that has been adapted to measure current subjective distress related to infertility risk. The survey has 15 questions, intended to collect the participant's assessment of intrusive thoughts (7 questions) and effortful avoidance of reminders about a distressing event (8 questions). The questions are answered on a 5-point scale ranging from "not at all" (1) to "extremely" (5). Total scores range from 15 to 75, with higher scores indicating greater distress (worse outcome). The outcome will be reported as the mean difference from baseline to 1 and 3 months, with standard deviation.

Timeframe: 3 months

Outcome 6 (Secondary)

Title: PROMIS Self-Efficacy (PROMIS-SE)

Description: The PROMIS General Self-Efficacy and Self-Efficacy for Managing Emotions subscales measure the degree to which people feel confident in managing various situations, problems, and events and confidence in managing difficult emotions. Questions will assess general self-efficacy in these domains and self-efficacy in managing fertility and family-building issues and emotions. The survey has 16 questions, intended to collect the participant's assessment of general self-efficacy (4 items), self-efficacy for managing fertility/family-building issues (4 items), self-efficacy for managing difficult emotions (4 items), and self-efficacy for managing difficult emotions related to fertility/family-building (4 items). The questions are answered on a 5-point scale ranging from (1) "I am not at all confident" to (5) "I am very confident." The outcome will be reported as the mean difference from baseline to 1 and 3 months, with standard deviation.

Timeframe: 3 months

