APPENDIX J: Impact of Events Scale (revised)*

Below is a list of difficulties people sometimes have after stressful life events. Please indicate how distressing each difficulty has been for you. Please answer in regards to your feelings DURING THE PAST SEVEN DAYS.

Please answer with respect to your fertility and possible risk for experiencing problems with family-building.

		Not at all	A little bit	Moderately	Quite a bit	Extremely
1.	Any reminder brought back feelings about it.	0	1	2	3	4
2.	I had trouble staying asleep.	0	1	2	3	4
3.	Other things kept making me think about it.	0	1	2	3	4
4.	I felt irritable and angry.	0	1	2	3	4
6.	I thought about it when I didn't mean to.	0	1	2	3	4
9.	Pictures about it popped into my mind.	0	1	2	3	4
10.	I was jumpy and easily startled.	0	1	2	3	4
14.	I found myself acting or feeling as though I was back at that time.	0	1	2	3	4
15.	I had trouble falling asleep.	0	1	2	3	4
16.	I had waves of strong feelings about it.	0	1	2	3	4
18.	I had trouble concentrating.	0	1	2	3	4
19.	Reminders of it caused me to have physical reactions, such as sweating, trouble breathing, nausea, or a pounding heart.	0	1	2	3	4
20.	I had dreams about it.	0	1	2	3	4
22.	I tried not to talk about it.	0	1	2	3	4

*Only the Intrusive Thoughts and Avoidance subscales of the IES-R are included.

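### Appendix J does not match the IES-R outcome: it prints 14 items coded 0-4 with one avoidance item, against 15 items coded 1-5 with eight in the outcome definition

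*Combined protocol and SAP*

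**What the plan says.** Section 4.0 lists the instrument as "Impact of Events Scale-Revised (IES-R) subscales, Appendix J: 15 items". Section 5.1 gives the split: "The Intrusive Thoughts (7 items) and Avoidance (8 items) subscales assess intrusive thoughts and effortful avoidance of reminders about a distressing event". Outcome 5 in section 5.4 repeats it as "intrusive thoughts (7 questions) and effortful avoidance of reminders about a distressing event (8 questions", codes each item from 1 to 5, and states: "Total scores range from 15 to 75, with higher scores indicating greater distress (worse outcome". The result is a change score: "The outcome will be reported as the mean difference from baseline to 1 and 3 months, with standard deviation". Section 5.2 places it among the secondary analyses: "Similar procedures will analyze changes in the IPQ-R, RCACS, PROMIS Self-Efficacy, and the IES-R as secondary outcomes".

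Appendix J is the form that section 4.0 points to. Its footnote reads "Only the Intrusive Thoughts and Avoidance subscales of the IES-R are included". The table above that footnote has 14 rows, numbered between 1 and 22 with gaps, and each response is coded 0 to 4. Item 22, "I tried not to talk about it", is the only row that describes avoiding something.

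**The concern.** The outcome definition and the form meant to produce it disagree on the number of items, their content and their coding. Content matters most. A wrong coding can be converted at analysis, but items that were not asked at baseline cannot be recovered. If the online form follows Appendix J, there is one item where the avoidance subscale should have eight. The Outcome 5 total would then be made up almost entirely of other symptoms while being reported as intrusion plus avoidance.

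**Working it through.** **Inputs.** From section 5.4, Outcome 5: 7 intrusion items, 8 avoidance items, coding 1-5, total 15-75. From Appendix J: the printed item numbers, their wording and the 0-4 coding.

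**1. The plan's own figure.** 7 + 8 = 15 items. Minimum 15 × 1 = 15; maximum 15 × 5 = 75. Outcome 5 is consistent within itself, and its item count agrees with sections 4.0 and 5.1.

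**2. Count of the printed form.** Items 1, 2, 3, 4, 6, 9, 10, 14, 15, 16, 18, 19, 20 and 22 make 14. The numbers 5, 7, 8, 11, 12, 13, 17 and 21 are absent, which is 8 gaps. The range is 14 × 0 = 0 to 14 × 4 = 56.

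**3. Content.** The documents contain no scoring key, so the sort uses only item wording and the section 5.1 description of avoidance. Item 22 is avoidance. The other 14 − 1 = 13 are not: they concern reminders, unwanted thoughts, images, dreams, sleep, irritability, startle, concentration and physical reactions.

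| | Sections 5.1 and 5.4 | Appendix J | Difference |
|---|---|---|---|
| Items | 15 | 14 | −1 |
| Avoidance | 8 | 1 | −7 |
| Not avoidance | 7 | 13 | +6 |
| Coding | 1-5 (section 5.4) | 0-4 | |
| Range | 15-75 (section 5.4) | 0-56 | |

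How many of the 13 count as intrusion, and how many belong to neither subscale, is a matter of judgement without the key. Moving items between those two groups does not change the 13.

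**4. Could rows have been lost when the table was converted to text?** Let L be the number of lost rows, from 0 to 8. The full form would have 14 + L items, at most 1 + L of them avoidance and at least 13 not avoidance.
- L = 1: 15 items, at most 2 avoidance.
- L = 7: up to 8 avoidance items, but 14 + 7 = 21 items in all.

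A 7 + 8 form needs exactly 7 items that are not avoidance. Restoring rows cannot bring 13 down to 7, so no value of L gives it.

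**5. Effect of the coding difference.** Recoding 0-4 as 1-5 adds 14 × 1 = 14 to every total on the printed form. If one coding is used at all visits, the difference between visits moves by 14 − 14 = 0, and its standard deviation does not change. Only absolute scores and the stated range are affected.

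**The case against.** The strongest reply is that the design is not in doubt. Sections 4.0, 5.1 and 5.4 agree on 15 items, sections 5.1 and 5.4 agree on the split, and the Appendix J footnote names the same two subscales. Only the printed table departs. Appendix B calls these questionnaires representations of the online ones, and other appendices are visibly loose copies: Appendix E routes respondents to Questions 34 and 35 in a questionnaire that ends at 17, and Appendix F has an unnumbered row. A faulty printed form is therefore weak evidence of a faulty REDCap form. This stands, and it is why the point is an inconsistency to be checked and not an established loss of data.

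It is also fair to say that the consequence is bounded. This is one secondary outcome in a single-arm pilot, it is defined as one total, and no test specific to avoidance is planned.

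The reply does not remove the conflict. Section 4.0 cites Appendix J as the instrument, and nothing else in the document lists the items, so a reader cannot tell from the plan what was asked.

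A reader might infer more than the documents support. One inference is that avoidance was never measured in this trial; the online form is not in the documents, so that cannot be concluded. Another is that the 0-4 against 1-5 difference biases the reported change; it does not if one coding is used throughout. A third is that the trial's rationale fails because avoidance is central to it. Section 2.0 speaks of avoiding fertility information, which is related to, but not the same as, the avoidance of reminders described for the IES-R in section 5.1.

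**Conclusion.** The inconsistency is real and should be resolved before Outcome 5 is analysed. As printed, Appendix J has 14 items and not 15, 1 avoidance item and not 8, 13 items that are not avoidance where 7 are specified, and a range of 0-56 and not 15-75. Lost rows do not explain it.

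The harm is conditional. If the REDCap form matches Appendix J, no avoidance subscale can be scored and the Outcome 5 total is not the measure that section 5.4 describes. If the REDCap form follows sections 4.0 and 5.1, the printed table needs correcting, and the response coding must be made to agree between Appendix J and section 5.4.

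The Decisional Conflict Scale primary outcome and the sample size are not touched. The conclusion rests on reading item 22 as the only avoidance item from its wording. It does not depend on how the other 13 are classified among themselves.

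**What to change.** 1. Check the built REDCap form against the scoring key of the cited instrument.
2. Reconcile sections 4.0, 5.1 and 5.4 (Outcome 5) and Appendix J on item list, items per subscale, response coding and total range, taking the counts from that key. For a final count of k items, the range is 0 to 4k if coded 0-4, or k to 5k if coded 1-5.
3. If the form is faulty and no participant has completed T1, correct the items before enrolment starts.
4. If participants have already answered a faulty form, keep the same item set and coding at T1, T2 and T3 for each participant and compute change only on items asked at both visits. Describe Outcome 5 by the items actually asked, not as intrusion plus avoidance. Changing items between one participant's visits would make that participant's change score uninterpretable.

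The cost is one form check and a protocol modification, which section 6.3 requires to be approved by the IRB before implementation. If the form was already used, there is the further cost of a narrower description of one secondary outcome. The final number of items cannot be given until the key is consulted.

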APPENDIX K: PROMIS Self Efficacy

General Self Efficacy

Please respond to each item by marking one box per row.

For the next set of questions, please read each sentence and rate your level of confidence in managing various situations, problems, and events.

Rate your level of confidence.	I am not at all confident (1)	I am a little confident (2)	I am somewhat confident (3)	I am quite confident (4)	I am very confident (5)
1. I can manage to solve difficult problems if I try hard enough.					
2. I am confident that I could deal efficiently with unexpected events.					
3. If I am in trouble, I can think of a solution.					
4. I can handle whatever comes my way.					

Now, thinking about your emotions related to your fertility and family-building, please respond to each question or statement by marking one box per row.

Rate your level of confidence about your emotions related to your fertility and family-building .	I am not at all confident (1)	I am a little confident (2)	I am somewhat confident (3)	I am quite confident (4)	I am very confident (5)
1. I can manage to solve difficult problems related to my fertility and/or family-building.					
2. I am confident that I could deal efficiently with unexpected events related to my fertility and/or family-building.					
3. If I am in trouble, I can think of a solution.					
4. I can handle whatever comes my way related to					

my fertility and/or family-building.					
--------------------------------------	--	--	--	--	--

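### Appendix K: one of the four fertility self-efficacy items lacks the fertility wording, and the block's stem asks about emotions, so that item may be answered in general terms

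*Combined protocol and SAP*

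**What the plan says.** Section 4.0 gives the self-efficacy questionnaire 16 items. Section 5.4, Outcome 6, divides them into four blocks of four, beginning with "assessment of general self-efficacy (4 items), self-efficacy for managing fertility/family-building issues (4 items" and ending with "self-efficacy for managing difficult emotions (4 items), and self-efficacy for managing difficult emotions related to fertility/family-building (4 items". Section 5.1 likewise treats general and fertility-specific self-efficacy as distinct content. Section 5.2 analyses change in PROMIS Self-Efficacy as a secondary outcome, in the same way as the Decisional Conflict Scale (DCS).

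Appendix K prints the fertility version of the general block as follows:

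- Item 1: "I can manage to solve difficult problems related to my fertility and/or family-building"
- Item 2: "I am confident that I could deal efficiently with unexpected events related to my fertility and/or family-building"
- Item 3: "If I am in trouble, I can think of a solution"
- Item 4: "I can handle whatever comes my way related to", with the fertility wording continuing after a page break

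The instruction above these items begins "Now, thinking about your emotions related to your fertility and family-building", and the row header repeats that frame. Appendix B notes that the printed questionnaires stand for the online versions.

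**The concern.** Item 3 is the only item in this block without the fertility wording, and the respondent has just answered the identical sentence in the general block. Its neighbours all name fertility, so a respondent could take the absence as a return to the general question. The stem adds to the doubt because it asks about emotions, while the items ask about problems, unexpected events and finding solutions. The general version of the same items has a stem about situations and problems.

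Objective 2 is to obtain preliminary effect sizes, and the website is meant to act on fertility and family-building matters. If item 3 is answered in general terms and general self-efficacy does not change, the block understates the change it is meant to capture. The understated estimate could then carry into later planning. In a total over all items, the same sentence would also count twice (2 of 16).

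**Working it through.** **Item count.** 4 + 4 + 4 + 4 = 16, which reproduces the figure in Sections 4.0 and 5.4.

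**Wording, side by side.** In the fertility version of the general block, 3 of 4 items (75%) carry the fertility wording. In the fertility version of the Managing Emotions block, also in Appendix K, 4 of 4 do. Together that is 7 of 8, which looks like an omission rather than a choice. It is not an effect of reading the PDF: item 3 is a complete sentence with its own check boxes, and only item 4 is split by the page break.

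**Size in the four-item block.** Let the three adapted items each change by c, and let item 3 change by f × c. The documents do not give f, so the full range from 0 to 1 is shown.

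Block mean change = (3c + fc)/4 = c × (3 + f)/4

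| f | Ratio to a fully adapted block |
|---|---|
| 0 | 3/4 = 0.75 |
| 0.5 | 3.5/4 = 0.875 |
| 1 | 4/4 = 1.00 |

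For illustration, with an assumed c of 0.5 points the block mean change is 0.375 at f = 0 and 0.50 at f = 1. The 0.5 is not in the documents.

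**Size in a 16-item total.** If the other 15 items all change by c, the ratio is (15 + f)/16: 0.94 at f = 0 and 1.00 at f = 1, a loss of at most 1/16. That bound depends on equal movement. If only the eight fertility items were to move, the ratio would be (7 + f)/8, or 0.875 at f = 0.

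**Standardised effect.** Section 5.2 reports Cohen's d, so the SD of change matters as well. Assume equal item SDs, a correlation r between changes on the adapted items, and a correlation s between changes on item 3 and on each of the others. At f = 0 the ratio of d to that of a fully adapted block is

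0.75 × √[(4 + 12r)/(4 + 6r + 6s)]

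- s = r: 0.75 for any r
- r = 0.3, s = 0: 0.75 × √(7.6/5.8) = 0.86
- r = 0.9, s = 0: 0.75 × √(14.8/9.4) = 0.94

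Over assumed r of 0.3 to 0.9, with s between 0 and r, the worst-case ratio for d is therefore 0.75 to 0.94.

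**The case against.** The strongest reply is that item 3 is not free-standing. The stem and the row header both direct the respondent to fertility and family-building. The plan relies on stem framing elsewhere: the items in Appendix J contain no fertility wording and depend wholly on an instruction to answer about fertility. A respondent who follows the frame answers item 3 as intended, and then f is near 1 and little or nothing is lost. This stands, and it is why the effect can only be given as a range. It does not remove the problem, because the frame names emotions, and because three neighbouring items repeat the fertility wording while this one does not.

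A reader might infer that a quarter of a registered subscale measures general self-efficacy and that any change is therefore diluted. The documents do not support that. They do not show how item 3 is answered. Outcome 6 is a single outcome: neither Section 5.2 nor Section 5.4 defines a separate score for this block, gives a score range, or says whether a total or the separate blocks will be reported. The 25% loss is the f = 0 end of the range, for a block score the plan does not define.

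Two further points stand. The slip may exist only in the appendix and not in the live form. And the documents do not show whether data have been collected, so rewording cannot be assumed to be harmless.

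**Conclusion.** The mismatch holds as a matter of text: Outcome 6 describes four items on fertility and family-building issues, while Appendix K prints three adapted items and one general item under a stem about emotions. Its effect is possible, not established. The retained share of the block's mean change is 0.75 to 1.00, assuming that the three adapted items move equally and that item 3 moves by between none and all of that amount. In a 16-item total the loss is at most about 6% if the other items move equally. The point is minor. It concerns one item of one secondary outcome and leaves the DCS primary outcome, the sample size in Section 5.3 and the feasibility aims untouched. It is still worth raising, because it changes what participants are asked and costs almost nothing to settle.

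**What to change.** 1. Compare item 3, the stem and the row header in the live REDCap form with Appendix K. If the live form is already right, correct the appendix only.
2. If the live form has the same wording and is not yet in use, add to item 3 the fertility and family-building phrase that items 1, 2 and 4 carry. Change the stem and row header to confidence in managing situations and problems related to fertility and family-building.
3. If the form is already in use, leave it unchanged from T1 to T3, because rewording part-way would break the within-person comparison. Report the block with and without item 3.
4. In either case, state in Section 5.2 or 5.4 how Outcome 6 is scored: one total, separate blocks, or both.

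The cost is one item, one stem and one header in the online form, or one additional descriptive line in the report if data collection has begun.
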